4.5 Sample Size

The primary outcome for this study is to assess medication adherence of patient after using mobile health application. Therefore, sample size for this randomized controlled trial is calculated using the continuous outcome formula below (Charan & Biswas, 2013; Wittes, 2002):

$$n_i = \frac{2(Z_{\alpha/2} + Z_{\beta})^2 P (1 - P)}{(P_1 - P_2)^2}$$

n_i = sample size required for each group ($i = 1,2$)

$Z_{\alpha/2}$ = Assumed type I error: α equal to 5%, then $Z_{0.05/2} = Z_{0.025} = 1.96$ (From Z table)

Z_{β} = Assumed power of 80% $Z_{\beta}=0.84$

$P_1 - P_2$ = Effect Size= Difference in the proportion of events in two groups

P = Total prevalence

Total Sample size needed: 388 per group

Note: Based on few past studies reported for non-adherence rate for patients in Malaysia is within 46.6% to 56% (Ting et al., 2019). Therefore, assumption of prevalence of chronic disease is 70%

of the adult and adherence rate of 50% is made. A systematic review showed that mobile app able to improve adherence by 7% to 40% (Pérez-Jover et al., 2019). Medication non-adherence rate of 50% is expected in control group and 40% is expected in intervention group. For a 10% absolute difference in medication non-adherence rate between control and intervention group, 388 patients per arm should be recruited in the study assuming a type I error of 5% and power of 80%.

N (number to enrol) * (1-% drop out) = desired sample size

Therefore N (number to enrol) = desired sample size / (1- % drop out)

$N = 388 / 0.80 = 485$ per group

Based on a systemic review published by Wood and colleagues found out there is a possibility of 20% loss of follow-up, drop out and those who are unable to meet the inclusion criteria (Wood et al., 2004). Therefore, a minimum sample size of 970 is needed in this study, with the number of 485 in each arm.

The sample size obtained from the primary outcome is too large and which might need to spend more time and manpower. Hence, the sample size calculation is repeated with the use of secondary outcome which is cost-effectiveness economic evaluation of the study. Glick (2011) formula is applied for the calculation of sample size as it incorporates all important economic evaluation informations such as difference in treatment costs and effects and willingness to pay threshold in a single formula.

$$n_i = \frac{2 \left(Z_{\alpha/2} + Z_{\beta} \right)^2 \left(Sd_c^2 + (W^2 Sd_Q^2) - (2 W p Sd_c Sd_Q) \right)}{(W\Delta Q - \Delta C)^2}$$

$n_i =$ sample size required for each group ($i = 1,2$)

$Z_{\alpha/2} =$ Assumed type I error: α equal to 5%, then $Z_{0.05/2} = Z_{0.025} = 1.96$ (From Z table)

$Z_{\beta} =$ Assumed power of 80% $Z_{\beta} = 0.84$

$W =$ Willingness to pay threshold

$p =$ Expected correlation between difference in costs (ΔC) and effects (ΔQ)

$\Delta Q =$ Expected difference in mean effects

$\Delta C =$ Expected difference in mean costs

$Sd_Q =$ Expected standard deviation for the effects

$Sd_C =$ Expected standard deviation for the costs

To our knowledge, there is no published study has evaluated the direct and indirect costs and quality of life associated with mobile health app for the management of non-communicable diseases. Therefore, the calculation is based on the assumption and few literature results. According to a study published in Malaysia, RM 2499.15 is required for the managing of patient complicated with diabetes and heart failure after the first event (Shafie & Ng, 2020). The cost from the study is adjusted according to Consumer Price Index 2022. The cost difference between treatment group is considered as around 30% as reported by the use of mobile app in the management of heart failure study (Cano Martín et al., 2014). A minimum difference of 0.01 is estimated in term of QALY in favour of mobile health app user. Sd_c and Sd_Q are assumed as RM1000 and 0.01 respectively. The willingness to pay threshold is set at RM 28,470 per QALY as reported by Lim et al. (2017). The correlation coefficient is set at minimum 0.1 as estimated from cost-effectiveness analysis of a mobile-based intervention for patients with type 2 diabetes mellitus conducted by Li et al. (2021). A number of 150 patients (75 per study group) is required to detect at least 80% power assuming a two-tailed test and alpha of 5% between treatment group. The sample size will be rounded up to 200 patients to account for a possibility of 20% attrition. The sample size obtained is corresponding to the sample size applied in Li et al. (2021) cost-effectiveness analysis study.

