4.6 Data Analyses

Intention to treat (ITT) analysis will be applied to evaluate the results to avoid any bias. The data analysis will be using the SPSS version 27. Data will be coded and analysed. Descriptive or categorical data will be expressed as mean \pm standard deviation (SD) unless otherwise stated. Student t-test will be used for analysis of normally distributed or continuous variables. Mann-Whitney test will be used for non-normally distributed data. Categorical data will be analysed using Chi-square or Fischer's exact test. A value of $P < 0.05$ is considered statistically significant.

The prevalence of medication compliant is quantified at 3 months and 6 months follow-up. Independent t-test or Mann-Whitney test will be used to compare MMAS score rankings between the intervention and control groups. Chi-Square test of independence will be used to determine the difference in number of patients with medication adherence between the intervention and control groups at 3 months and 6 months follow-up. Ordinal logistic regression, with the MMAS adherence score ranking, will be used to examine the association between intervention and control groups.

For the perception and satisfaction towards the app, the frequency and percentage of respondents in each category (strongly disagree to strongly agree) will be calculated. The median of each statement will then be calculated to give an overview of perception and satisfaction towards the CareAide® app. Chi-square, Mann-Whitney U, Kruskal Wallis, Chi-square tests and logistic regression will be used where appropriate. The open-ended question will be analysed using thematic analysis as proposed by Braun and Clarke (2012). Codes will be assigned to the data to describe the content. After the coding is completed, themes will be generated, reviewed, and named. Linear regression analysis will be conducted to determine the independent predictors of HRQoL.

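### The protocol calculates 970 patients for its primary adherence outcome but adopts 200, where power for the planned 50% versus 40% comparison is only about 24% to 29%

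*Combined protocol and SAP*

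**What the plan says.** Sections 3.1 and 4.4.1.1 make medication adherence the primary objective and outcome, measured by MMAS-8 and by proportion of days covered (PDC) at baseline, 3 months and 6 months.

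Section 4.5 sizes the trial on a binary version of that outcome: "Medication non-adherence rate of 50% is expected in control group and 40% is expected in intervention group". With a two-sided 5% level and 80% power this gives 388 per arm. After a 20% allowance for loss it concludes: "Therefore, a minimum sample size of 970 is needed in this study, with the number of 485 in each arm".

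The same section then withdraws from that number on grounds of resources ("The sample size obtained from the primary outcome is too large and which might need to spend more time and manpower") and repeats the calculation for cost-effectiveness, a secondary outcome. The result is: "A number of 150 patients (75 per study group) is required to detect at least 80% power assuming a two-tailed test". The final step is: "The sample size will be rounded up to 200 patients to account for a possibility of 20% attrition".

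Section 4.6 keeps the binary adherence analysis at both follow-up times: "Chi-Square test of independence will be used to determine the difference in number of patients with medication adherence". It also plans a comparison of scores: "Independent t-test or Mann-Whitney test will be used to compare MMAS score rankings between the intervention and control groups". No part of the text available gives power, a detectable difference or expected precision for adherence at 200 patients.

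**The concern.** Two sample sizes stand in the current text of section 4.5. One is called the minimum needed, and the other, about a fifth of it, will be enrolled. The 80% power attached to the adopted size belongs to the cost-effectiveness calculation, but a reader could easily carry it over to the primary outcome. The plan gives the reason for the reduction but not its consequence.

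What is at stake is the first research question, whether the app improves adherence. P < 0.05 is the only decision criterion in section 4.6. If the app works as well as the sponsor assumed, the likeliest result of the binary comparison at 200 is non-significance. If the low power was not stated beforehand, that result could be read as evidence that the app does nothing.

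**Working it through.** **Inputs.** From section 4.5: non-adherence 50% (control) and 40% (intervention), two-sided 5% (z = 1.96), 80% power (z = 0.84), 20% loss, adopted total 200. From section 4.1: 1:1 allocation. So 100 per arm are enrolled, and 100 × 0.80 = 80 per arm are evaluable if the planned loss occurs.

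**Reproducing the plan's figure.** With the average proportion P = (0.50 + 0.40)/2 = 0.45, the plan's formula gives

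n = 2 × (1.96 + 0.84)² × 0.45 × 0.55 / 0.10² = 388.08 per arm.

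Then 388/0.80 = 485 per arm, and 2 × 485 = 970. All three stated figures reproduce.

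**Power at the adopted size.** For the two-proportion test with a pooled variance under the null,

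power ≈ Φ[(0.10 − 1.96 × SE₀)/SE₁], where SE₀ = √(2 × 0.45 × 0.55/n) and SE₁ = √((0.25 + 0.24)/n).

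- n = 80: SE₀ = 0.0787 and SE₁ = 0.0783, so Φ[(0.10 − 0.1542)/0.0783] = Φ(−0.69) ≈ 0.24.
- n = 100: SE₀ = 0.0704 and SE₁ = 0.0700, so Φ[(0.10 − 0.1379)/0.0700] = Φ(−0.54) ≈ 0.29.
- n = 388: 0.80, as the plan intends.

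Exact enumeration of the uncorrected chi-square test gives 0.238 (n = 80) and 0.310 (n = 100), so the approximation is adequate.

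**Detectable difference and precision.** Solving the same expression for 80% power, starting from 50%, gives 21.5 points (n = 80) and 19.3 points (n = 100), about twice the planned 10. The 95% confidence interval half-width, 1.96 × √(0.49/n), is 15.3 points (n = 80) and 13.7 points (n = 100). An estimate of exactly 10 points would have an interval that includes zero.

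**Other effect sizes.** The plan cites a review in which apps improved adherence by 7% to 40%. Reading these as absolute points (an assumption), power from a 50% control rate is:

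| Difference (points) | 80 per arm | 100 per arm |
|---|---|---|
| 7 | 14% | 17% |
| 10 (planned) | 24% | 29% |
| 15 | 48% | 58% |
| 20 | 74% | 83% |
| 25 | 91% | 96% |

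**Control rate.** Over the 46.6% to 56% non-adherence range cited in section 4.5, with a 10-point difference, power is 24% to 25% at 80 per arm and 29% to 30% at 100 per arm. The result does not depend on exactly 50%.

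**The case against.** The sponsor was open about the reduction. The assumptions and both sample sizes are printed, and a statistician could derive the power. Limited time and staff are a legitimate reason for a smaller trial. This is why the recommendation keeps 200. It does not remove the need to state what 200 can show.

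The binary test is also not the only adherence analysis. Section 4.6 compares MMAS scores and fits an ordinal regression, and these may be more powerful. That is fair, and the 24% to 29% applies to each binary comparison, not to every adherence analysis. However, the documents give no SD or target difference for MMAS-8 or PDC, so the plan cannot claim adequate power by that route. The only adherence effect it specifies is the binary one.

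The true effect may exceed 10 points, as the cited range allows. At 20 points power would be 74% to 83%. But 10 points is the plan's own value, and it was not changed when the sample size was.

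Finally, a 50% control rate taken from general patient figures may not suit patients selected for MMAS below 6. If non-adherence among controls were 80% or 90% (illustrative values, not in the documents), power for 10 points would be 31% or 42% at 80 per arm and 37% or 51% at 100 per arm. The figures put into the plan should therefore be labelled as conditional on 50% versus 40%. The shortfall remains in every case.

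**Conclusion.** The concern holds and must be fixed. At the adopted size the plan does not deliver the size and power it sets for its own primary outcome, and it does not say so. Power for 50% versus 40% is about 24% (80 per arm) to 29% (100 per arm) against the 80% planned, so each such test would miss a true 10-point effect about 7 times in 10 or more. Power reaches 80% only at about 19 points with 100 per arm, or 21.5 points with 80.

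This rests on the plan's own rates, a two-sided 5% level, equal arms, and between 80 and 100 evaluable patients per arm. It is confined to the binary comparison. Power for the MMAS score comparison cannot be computed from the documents.

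**What to change.** **Required, in section 4.5.** Keep 200. Replace the statement that 970 is needed with one saying that 970 was calculated for the primary outcome and not adopted. Then give the figures at 200: for non-adherence of 50% versus 40%, power of about 24% (80 per arm) to 29% (100 per arm), and a difference detectable with 80% power of about 21.5 to 19 points. Say that the 80% power refers only to the cost-effectiveness calculation.

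**Required, in section 4.6.** Add one sentence: a non-significant binary adherence result will be reported with its 95% confidence interval and described as inconclusive about a 10-point effect.

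**Optional.** Name one continuous adherence measure (MMAS-8 or PDC) at 6 months, adjusted for its baseline value, as the main comparison. With 80 per arm the detectable difference is 2.8 × √(2/80) = 0.44 SD unadjusted. Multiplying by √(1 − r²) gives 0.42, 0.38 or 0.32 SD for a baseline correlation of 0.3, 0.5 or 0.7. These correlations are assumptions. For MMAS-8 the true value may be low, because entry is restricted to scores below 6. Without an SD, these figures cannot be compared with the 10-point target.

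**Query for the sponsor.** Is a 50% control rate suitable for patients selected for MMAS below 6?

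**Cost.** The required part is wording only, with no extra patients or visits; the price is that low power for adherence is stated openly. The optional part changes the analysis plan, because one measure and one time point must be chosen.

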4.6 Data Analyses

Intention to treat (ITT) analysis will be applied to evaluate the results to avoid any bias. The data analysis will be using the SPSS version 27. Data will be coded and analysed. Descriptive or categorical data will be expressed as mean \pm standard deviation (SD) unless otherwise stated. Student t-test will be used for analysis of normally distributed or continuous variables. Mann-Whitney test will be used for non-normally distributed data. Categorical data will be analysed using Chi-square or Fischer's exact test. A value of $P < 0.05$ is considered statistically significant.

The prevalence of medication compliant is quantified at 3 months and 6 months follow-up. Independent t-test or Mann-Whitney test will be used to compare MMAS score rankings between the intervention and control groups. Chi-Square test of independence will be used to determine the difference in number of patients with medication adherence between the intervention and control groups at 3 months and 6 months follow-up. Ordinal logistic regression, with the MMAS adherence score ranking, will be used to examine the association between intervention and control groups.

For the perception and satisfaction towards the app, the frequency and percentage of respondents in each category (strongly disagree to strongly agree) will be calculated. The median of each statement will then be calculated to give an overview of perception and satisfaction towards the CareAide® app. Chi-square, Mann-Whitney U, Kruskal Wallis, Chi-square tests and logistic regression will be used where appropriate. The open-ended question will be analysed using thematic analysis as proposed by Braun and Clarke (2012). Codes will be assigned to the data to describe the content. After the coding is completed, themes will be generated, reviewed, and named. Linear regression analysis will be conducted to determine the independent predictors of HRQoL.

An economic evaluation will be conducted from a payer and societal perspective. Costs and outcomes will be discounted at 3% per year (Shafie et al., 2019) as the results will be extrapolated to examine costs and outcome over a year.. Cost effectiveness analysis will be estimated based on the results of cost data and EQ-5D-5L to calculate the incremental cost per quality adjusted life year (QALY) gained. Total incremental cost effectiveness ratio (ICER) will be calculated by dividing the difference between the cost of CareAide intervention group and control group by the difference between the QALYs of CareAide intervention group and control group. Sensitivity analysis will be performed by bootstrapping technique to ensure or examine the robustness of ICER. Then, cost effectiveness acceptability curve (CEAC) will be created to estimate the proportion of the result being cost-effective in relation to the Willingness-to-Pay (WTP) threshold.

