4.4.1.1 Primary outcome

Medication adherence: CareAide® effectiveness is measured with a medication adherence tool at baseline and follow-up time periods at 3 months and 6 months using Morisky Medication Adherence Scale-8 (MMAS-8) and proportion of days covered (PDC). The primary outcome of the study is medication adherence, which is assessed using the 8-item Morisky Medication Adherence Scale (MMAS-8) and the Proportion of Days Covered (PDC) method. Measurements are taken at baseline and at two additional time points, with a 3-month interval following the intervention. MMAS-8 is a licensed validated questionnaire to assess medication adherence, where a higher score represents higher medication adherence and vice versa. Comprising of 8 items, the score ranges from 0 to 8, where a higher score represents a higher medication adherence. The internal consistency (Cronbach's alpha) of MMAS-8 is 0.83 along with a sensitivity of 93% and a specificity of 57%. The PDC method utilises pharmacy refill records (Raebel et al., 2013). The PDC can be calculated as below (Hess et al., 2006; Raebel et al., 2013; Pednekar et al., 2019):

$Nm/Nd \times 100\%$

Where N_m denotes the number of days covered by the medication while N_d meant the number of days in the study period. The patients are considered to be adherent if their PDC scores are ≥ 0.8 or 80% (Karve et al., 2009). The prescription refill data was extracted from outpatient/hospital database.

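### Intention to treat is stated without any method for missing outcomes, so MMAS-8, QALYs and questionnaire costs default to complete cases; refill-based PDC could keep nearly everyone, but the plan does not say it will

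*Combined protocol and SAP*

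**What the plan says.** - **Principle.** Section 4.6: "Intention to treat (ITT) analysis will be applied to evaluate the results to avoid any bias".
- **Adherence analyses.** Section 4.6 gives three.
  - For the questionnaire score: "Independent t-test or Mann-Whitney test will be used to compare MMAS score rankings between the intervention and control groups".
  - For the binary outcome, at each of the two follow-up times: "Chi-Square test of independence will be used to determine the difference in number of patients with medication adherence".
  - As a regression model: "Ordinal logistic regression, with the MMAS adherence score ranking, will be used to examine the association between intervention and control groups".
- **Economic analysis.** Section 4.6: "Sensitivity analysis will be performed by bootstrapping technique to ensure or examine the robustness of ICER".
- **Data sources.** Section 4.4.1.1 has two adherence measures. For both, "Measurements are taken at baseline and at two additional time points". MMAS-8 is a questionnaire and needs contact with the patient. For the other, "The PDC method utilises pharmacy refill records", held in the outpatient or hospital database. PDC of at least 80% is the only cut-off given for calling a patient adherent on the outcome. Section 4.4.1.2 collects EQ-5D-5L, SF-36 and patient-reported costs by interview or questionnaire.
- **Attrition.** Section 4.5: "The sample size will be rounded up to 200 patients to account for a possibility of 20% attrition". Section 4.3.3 does not replace withdrawn participants, and it lists non-compliance with study procedures among the possible reasons for discontinuation.

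The plan does not define an ITT analysis set, an imputation or non-responder rule, a repeated-measures model, or a sensitivity analysis for missing data.

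**The concern.** Intention to treat settles which patients belong in each arm. It does not supply values for patients whose outcome was never observed. Each adherence analysis in section 4.6 needs a value for every patient it includes. If no rule is stated, the routine result is that patients without a value are left out. Resampling the observed costs and QALYs describes sampling uncertainty and does not restore the missing patients.

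There is reason to think the losses could be related to outcome. The trial is open-label, only the app arm is asked to take up an app, and the outcome is adherence itself. Patients who stop using the app or stop answering may also be the less adherent. If so, the comparison among responders is biased while the text says that bias has been avoided. A larger N narrows the confidence interval around that biased figure.

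**Working it through.** **1. The plan's own figures (section 4.5).**

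- Adherence calculation, with 50% and 40% non-adherence and mean P = 0.45: 2 × (1.96 + 0.84)² × 0.45 × 0.55 / 0.10² = 388.1, the stated 388 per group. With 20% loss, 388 / 0.80 = 485.
- Adopted calculation (net benefit). The inputs are W = 28,470, SDs of RM 1000 and 0.01, correlation 0.1, QALY difference 0.01, and cost difference 30% of RM 2499.15 = RM 749.7.
  - Variance term: 1000² + 284.7² - 2 × 28,470 × 0.1 × 1000 × 0.01 = 1,024,114.
  - n = 15.68 × 1,024,114 / (284.7 - 749.7)² = 74.25, so 75 per group. This needs the cost difference entered as an added cost in the app arm; that is a separate matter and does not affect this point.
- 150 / 0.80 = 187.5, so 188, which the plan rounds up to 200.

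**2. Patients left after 20% loss.** 200 × 0.80 = 160, or 80 per arm, against the adopted requirement of 75. About 40 randomised patients would lack contact-based outcomes.

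**3. Effect of the missing-data rule.** Assumptions: 100 per arm, 20 missing in each, and observed patients at the planned rates, so 40/80 non-adherent in control and 32/80 in the app arm. Differences are app minus control; negative favours the app.

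| Handling of the 20 missing per arm | Control | App | Difference (points) |
|---|---|---|---|
| Complete cases | 40/80 = 50% | 32/80 = 40% | -10 |
| All missing non-adherent | 60/100 = 60% | 52/100 = 52% | -8 |
| Extreme against the app (control missing adherent, app missing non-adherent) | 40/100 = 40% | 52/100 = 52% | +12 |
| Extreme for the app (control missing non-adherent, app missing adherent) | 60/100 = 60% | 32/100 = 32% | -28 |

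**4. When there is no bias.** Let m be the share lost in an arm and g the adherence of its completers minus that of its losses. Complete-case adherence exceeds the full-arm value by m × g. The bias in the between-arm difference is m × g in the app arm minus m × g in control. It is zero when m and g are the same in both arms.

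**5. Which outcomes are exposed.**

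- MMAS-8, EQ-5D-5L and QALYs, SF-36 and questionnaire costs need contact, so they are exposed.
- PDC can be computed for a patient who no longer attends, unless consent is withdrawn or refills move elsewhere. The chi-square on PDC of at least 80% need not lose these patients, but section 4.6 does not say on whom it will be run.

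**The case against.** The strongest reply is that section 4.6 is silent rather than wrong. The listed tests can be run on imputed values, or with missing counted as non-adherent, and either would fit the ITT sentence. PDC, half of the primary outcome, does not depend on a visit. The plan also limits loss: section 4.4.1.2 allows phone interviews, and section 4.3.3 has documented attempts to reach patients lost to follow-up. All of this stands, and it confines the point to contact-based outcomes and to the absence of a stated method.

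A reader might infer more, and the documents do not support it:

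- **That the named tests can use only patients seen at that visit.** They default to this when no rule is given; nothing about the tests requires it.
- **That the plan expects to lose 20%.** Section 4.5 calls it a possibility, and in the adherence calculation the 20% also covers patients who fail the inclusion criteria.
- **That app-arm adherence is overstated by 4 to 8 points.** This takes 20% loss and a gap of 20 to 40 points in the app arm (0.20 × 0.20 and 0.20 × 0.40), with no gap in control. The documents give no source for either condition.
- **That 3-month data are discarded.** They are analysed at 3 months; they only fail to inform the 6-month comparison.
- **That a QALY needs every interview.** QALYs are planned over 3 as well as 6 months, so baseline and 3-month data give a 3-month QALY.
- **That attrition leaves too few patients.** Eighty per arm exceeds the adopted 75.

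**Conclusion.** The point holds for MMAS-8, QALYs and questionnaire costs: the ITT statement has no missing-data method behind it, and raising N does not supply one. For PDC the gap is one sentence saying that all randomised patients will be scored.

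The size cannot be fixed in advance. Under equal 20% loss, counting all missing as non-adherent moves the planned contrast by only 2 points. The extremes span 40 points and include a change of sign, but they are bounds, not forecasts. The illustration rests on assumed equal loss by arm and on the 50% and 40% rates from the adherence calculation, which the plan set aside for its final N. This is a risk of bias, not a shortfall against the adopted sample size. It should be corrected before analysis because the better methods use data the trial already collects.

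**What to change.** 1. **MMAS-8.** Make the main comparison a mixed model for repeated measures over baseline, 3 and 6 months with arm-by-visit terms, including every randomised patient with any score. Keep the t-test, Mann-Whitney test and ordinal regression as supportive.
2. **PDC.** State that PDC, and the chi-square on PDC of at least 80%, will be computed from refill records for all randomised patients regardless of visit attendance, unless consent is withdrawn.
3. **EQ-5D-5L and costs.** Use multiple imputation by arm, combined with the bootstrap of the ICER.
4. **Sensitivity.** Items 1 and 3 assume data missing at random, which is the assumption in doubt. Impute missing MMAS-8 scores and QALYs, then worsen the app-arm imputed values until the conclusion changes. For binary adherence, add an analysis with missing counted as non-adherent.

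The cost is revised text in section 4.6 and modest extra analysis with standard procedures. The estimate may come out slightly less favourable to the app. No new data are needed.

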4.0 Methodology

4.1 Study Design

A 3- and 6- month open-label multicentre randomized controlled trial with two parallel groups will be conducted. This study will take place in the outpatient setting of the three hospitals [i.e., Hospital Putrajaya, Hospital Pulau Pinang and Universiti Malaya Medical Center (UMMC)) in Malaysia]. Standard chronic disease treatments will be given to both groups of participants, but the CareAide ® app will be provided for the experimental group during the trial. Both groups will be allocated to 1:1 ratio. Randomization number will be generated by using online number generated programme. Consultants reviewing patients at medical, cardiology, diabetes mellitus and asthma clinics will provide referral and notify independent researchers for eligibility and group assignments. Eligible patients will then be instructed to see pharmacists/researchers at outpatient pharmacies to refill their prescriptions and subsequently enrol in the assigned study group either to receive an intervention with CareAide® or to receive normal clinical care. Information and training on the app will be provided by these researchers to the participants.

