4.4.1.2 Secondary outcomes

Fasting blood sugar, HbA1C, cardiovascular events (heart failure admission, mortality), asthma control and blood pressure, hospitalizations and emergency visits measurements will be based on the clinics attended by the participants. Health care utilization, quality of life and health care expenditures will be measured for all the participants.

i. Data Collection

Data on patients' sociodemographic, resources consumptions such as direct and indirect medical costs and health quality of life (HRQoL) will be collected.

ii. Sociodemographic

Data such as socio-demographics (age, sex, education level, occupation, income, and religion), will be collected via face-to-face interview or phone interview via a structured and validated questionnaire.

iii. Direct Medical Cost

This study will apply a bottom-up micro costing approach for direct cost estimation. Healthcare costs such as outpatient visits, medicine use, hospitalization, diagnostic and laboratory test costs will be gathered in this study for direct cost estimation of chronic diseases. Costs for outpatient visits, hospitalization, diagnostic and laboratory tests will be valued based on the MOH Full Paying Patient Tariff Schedule of fees for a foreigner patient scheme provided by the Financial Department for Ministry of Health Hospitals. Medication utilization costs will be estimated from the National Price List of Medicines provided by the Procurement Unit of the Pharmacy Department. Costs of medicine per patient will be calculated by total drugs supplied for a patient multiplied by the average acquisition cost price obtained of the hospital. All costs will be valued in Malaysia Ringgit (MYR).

iv. Indirect Medical Cost

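### No analysis is named for hospitalisations, emergency visits and heart-failure admissions; the generic tests that remain ignore follow-up time, and no rule covers patients followed for only part of the six months

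*Combined protocol and SAP*

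**What the plan says.** Section 4.4.1.2 lists the event outcomes among others: "cardiovascular events (heart failure admission, mortality), asthma control and blood pressure, hospitalizations and emergency visits measurements will be based on the clinics attended". It gives no data source, time window or summary measure for the events.

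Section 4.6 names methods for adherence, app perception and satisfaction, quality of life and the economic evaluation. For everything else it gives a rule by data type. The first part reads "Student t-test will be used for analysis of normally distributed or continuous variables". The part for other data reads "Mann-Whitney test will be used for non-normally distributed data. Categorical data will be analysed using Chi-square", with Fisher's exact test as the alternative for categorical data. No rate model, follow-up-time offset, time-to-event method or censoring rule appears anywhere in the document.

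On the analysis set, section 4.6 says "Intention to treat (ITT) analysis will be applied to evaluate the results to avoid any bias", with no rule for missing or partial outcome data.

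Incomplete follow-up is foreseen. The sample in section 4.5 is enlarged "to account for a possibility of 20% attrition". Section 4.3.3 lists withdrawal and loss to follow-up, and says that those who withdraw are not replaced. Section 4.1 describes the design: "A 3- and 6- month open-label multicentre randomized controlled trial with two parallel groups will be conducted".

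**The concern.** Admissions and emergency visits accumulate over time at risk. A patient seen for two months has had a third of the opportunity for an event that a patient seen for six months has had. A test that sees only a count, or a yes/no, treats the two alike unless the plan says otherwise.

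The trial is open-label, and section 4.3.3 gives non-compliance with study procedures as a possible reason for discontinuation. Only the intervention arm has an app to download and use, so that arm has an additional route to loss. The documents do not show that loss will differ by arm, but they supply a mechanism. If the app arm lost more patients, its shorter observation would look like fewer admissions, in favour of the app. If the control arm lost more, the bias would run the other way.

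**Working it through.** **Inputs from section 4.5.** The plan states no figure for the event outcomes. Its attrition arithmetic can be reproduced: 388 / 0.80 = 485 per group for the adherence calculation, as stated. For the cost-effectiveness calculation, 150 / 0.80 = 187.5, so 188, which the plan rounds up to 200. I use 20% overall loss and 200 / 2 = 100 per arm.

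**Assumptions, not in the documents.** Six-month event risk q from 10% to 40%, the same in both arms (no effect); constant event rate; loss spread evenly over six months and unrelated to outcome; events before loss counted; patients lost before an event scored event-free.

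**Formulas.**
- Rate over six months: λ = −ln(1 − q).
- Chance that a lost patient has an event before loss: u = 1 − (1 − e^(−λ)) / λ.
- Observed risk with loss proportion d: (1 − d)q + d·u.
- Rejection rate: two-sided pooled z-test, equivalent to chi-square without continuity correction, 100 per arm.

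**Example, q = 20%.** λ = 0.2231 and u = 1 − 0.20 / 0.2231 = 0.104.
- Loss 20% in both arms: 0.80 × 0.20 + 0.20 × 0.104 = 0.181 in each, ratio 1.00.
- Loss 30% app, 10% control: 0.70 × 0.20 + 0.30 × 0.104 = 0.171 against 0.90 × 0.20 + 0.10 × 0.104 = 0.190, ratio 0.899.

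| True risk, both arms | Observed, 20% loss each | Type I error | Observed app / control, 30% vs 10% loss | Ratio | Type I error |
|---|---|---|---|---|---|
| 10% | 9.0% | 5.0% | 8.5% / 9.5% | 0.897 | 5.7% |
| 20% | 18.1% | 5.0% | 17.1% / 19.0% | 0.899 | 6.4% |
| 30% | 27.2% | 5.0% | 25.8% / 28.6% | 0.901 | 7.3% |
| 40% | 36.3% | 5.0% | 34.5% / 38.2% | 0.904 | 8.4% |

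With equal loss the comparison is unbiased, but each risk is understated by about 10% of its value (9.0 against 10; 36.3 against 40). An extreme split of 40% against 0% gives ratios of 0.80 to 0.82 and type I error of 7.7% to 18.9%.

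**Mean counts instead of yes/no.** Mean exposure is 1 − d/2 of the full period. With 30% against 10% loss the ratio of expected counts is 0.85 / 0.95 = 0.895; with 25% against 15% it is 0.875 / 0.925 = 0.946. Dividing each count by its exposure returns 1.00, which is what the offset does.

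**Leaving lost patients out.** Under the same assumptions this creates no false difference. With 20% loss it leaves 80 of 100 per arm, so standard errors grow by √(100/80) = 1.118, about 12%.

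**The case against.** Four readings are stronger than the documents allow.

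- A reader might infer that the plan assigns chi-square or rank tests to these outcomes. It does not. It offers a generic menu that also contains the t-test. The defect is an omission with an unsuitable default.
- A reader might infer that lost patients will be counted as event-free or discarded. Neither is stated. Discarding sits badly with the declared intention-to-treat analysis, and imputation is neither planned nor excluded. But intention to treat fixes who is analysed and in which arm; it does not say how a patient lost at month 1 is scored.
- A reader might infer that the economic evaluation is left without a rate difference that it needs. It uses none. Hospitalisation is costed bottom-up (section 4.4.1.2, item iii), and the cost-effectiveness ratio is formed from differences in costs and QALYs and bootstrapped (section 4.6).
- A reader might take the ratio of 0.90 as the expected bias. The documents give one overall attrition figure and no split by arm.

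The data source also matters. Section 4.4.1.1 takes refill data from the hospital database, and section 5.1 mentions information extracted from medical records. If admissions come from records, those at the study hospital may be captured after visits stop. If they come from the three-month recall described in section 4.4.1.2, item iv, a patient lost at month 1 has no post-baseline report: the outcome is missing, not zero. An offset running to last contact could then count time in which nobody asked about events.

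Finally, comparing the proportion with an event over a fixed six months is acceptable if partial follow-up is handled by a stated rule. All of this stands, and it shapes the remedy. It does not supply the missing rule.

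**Conclusion.** The point holds as a gap in specification. The only between-group tests that can reach these outcomes take no account of follow-up time, 20% attrition is expected, and no rule covers partial follow-up.

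If loss is equal and non-informative, the harm is limited to understated risks or lost precision, and the 5% level is kept. Material bias needs unequal or informative loss, which is plausible in an open-label app trial but not shown. The figures for unequal loss rest on the assumed split, event risks and scoring. The type I error also depends on sample size: it would be closer to 5% where an outcome is collected only in patients of certain clinics, and further from it in a larger trial.

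These are secondary outcomes, so the primary conclusion on adherence is not affected. The change should still be made, because it is cheap and removes a choice otherwise made after the data are seen.

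**What to change.** In section 4.6, state that hospitalisations, emergency visits and heart-failure admissions will be analysed by negative binomial regression (or Poisson regression with robust standard errors), with the log of ascertained follow-up time as offset, and reported as a rate ratio with 95% confidence interval. In addition:

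- State in section 4.4.1.2 whether events come from hospital records or patient report.
- Define ascertained time to match: to the last completed 3- or 6-month questionnaire, or to the end of the record search.
- Include every randomised patient for whom the outcome is collected, given that section 4.4.1.2 ties collection to the clinic attended.
- End time at risk at death, and report deaths by arm beside these results.
- State that the offset corrects only for non-informative loss.

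The cost is SAP wording, one added date on the case report form (last ascertainment; section 4.3.3 already has completion status documented) and slightly more analysis work. The models are available in standard software.
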